
5	If "yes", indicate whether being recorded is required in order to participate and explain this in the consent document or guide:			\boxtimes
6	Does the study involve conducting research activities online?		\boxtimes	
7	Is the study designed to be implemented in phases, where fully describing one phase is dependent upon the outcome of another?		\boxtimes	
0	IRB approval must be obtained prior to initiating each phase.			
SECTION	N 21 - Compensation	Yes	No	N/A
1	Describe any compensation or incentives for participants:			
	Subjects will receive \$125 for each completed cycle. Subjects who discontinue the study early will be paid an amount pro-rated to the percentage of total blood samples completed. The amount will be determined by multiplying the number of study blood samples completed by \$11.36. Subjects also receive up to \$10 worth of breakfast foods and beverages on day 1 of each cycle.			
•	Include details concerning the conditions under which research participants would receive partial payment or no payment at all (e.g., withdrawing early from the study)			
SECTION	N 22 - Costs	Yes	No	N/A
1	Describe any costs to participants that are associated with the study (e.g., parking, travel, etc.):			
	Subjects are responsible for transportation to and from the study site. A parking space outside of LPSC is reserved for study subjects during their visits.			
0	This section should not include costs incurred by the study team or the study.			
SECTION	N 23 - Education Records	Yes	No	N/A
•	Education Record is defined by FERPA as a range of information about a student that is maintained in schools in any recorded way, such as handwriting, print, computer media, video or audio tape, film, microfilm, and microfiche.			
1	Does the study involve the use of student education records?		⊠ Skip to section 24	

1a	If yes, list all data to be used (e.g. course grades, assignments, GPA, video-recordings of class activities, etc.):			
2	Are any of the education records related to OSU students?			
3	How will education records will be accessed or obtained (e.g., provided by class instructor; request will be submitted to the Office of the Registrar; etc.)?			
Q	Information on Feasibility Determinations and Data Requests through the Office of the Registrar			
SECTION	N 24 - Drugs or Biologics	Yes	No	N/A
Q	Guidance and decision trees on Drugs, Biologics, and Dietary Supplements			
1	Are one or more drugs or biologics being studied as part of this project?		□ Skip to section 25	
2	Drug Name (include generic and trade name, if applicable):			
	[7- ¹⁴ C]-benzo[a]pyrene (BaP), specific activity 27 μCi/μmol			
3	Approval Status (e.g., FDA Approved, FDA Approved/Unapproved Use, not FDA approved):			
	not approved for therapeutic use; this protocol is an amendment to FDA IND 117175 (see IRB Protocol 8233 for FDA correspondence)			
4	Has an IND application been submitted to the FDA?	\boxtimes		
5	If no, provide justification:			
6	Chemical formula:			
	C ₂₀ H ₁₂			
7	Dosage strength(s):			

	50 ng (alone or with 1250 ng phenanthrene)		
8	Rationale for choosing the drug or substance dose:		
*	The U.S. EPA is considering a model of risk assessment for PAH mixtures that utilizes the Relative Potency Factor (RPF) approach, derived from animal studies ⁶ . BaP is the reference compound and has an RPF of 1. The accuracy of the RPF approach is based on the assumption that the interaction between all PAHs is additive (same Mechanism of Action or MOA) and that high-dose animal data can model human exposure at environmentally relevant levels (orders of magnitude lower than the animal studies). Until now, it has not been possible to test these caveats in humans. The administration of the binary mixture of [¹⁴ C]-BaP plus phenanthrene will allow us to better determine PAH risk assessment and pharmacokinetics at environmentally relevant levels of exposure in humans.		
9	Method/route of administration:		
	Subjects will consume one capsule containing either [¹⁴ C]-BaP alone or [¹⁴ C]-BaP plus phenanthrene by mouth with 100 mL of water.		
10	Mechanism of action:		
	BaP is not a therapeutic, so the mechanism of action described involves the current understanding of BaP carcinogenesis. The most well accepted mechanism for BaP carcinogenesis involves metabolic activation ²³ . Bioactivation to the ultimate carcinogen is initiated by epoxygenation at the 7,8-position. The epoxide is hydrolyzed by the action of the enzyme epoxide hydrolase and a second epoxygenation produces the ultimate mutagenic and carcinogenic metabolite, the BaP-7,8-dihydrodiol-9,10-epoxide. The (+)-anti-BaP-7,8-dihydrodiol-9,10-epoxide metabolite is the most mutagenic and carcinogenic form of BaP. The metabolite is formed by oxidative metabolism by cytochrome P450 enzymes (CYPs) enzymes, primarily in the liver (also to some degree in lung and GI). The epoxide is chemically unstable and has been shown to react with the N2 position in guanine in DNA which can lead to mutations in genome sequence.		
11	Known drug interactions:		
	Not applicable at this microdose		
12	Manufacturer/Sponsor:		
	American Radiolabeled Inc. (ARC, custom synthesis)		
13	Manufacturer/Sponsor Location:		

5

Diet

	St. Louis, Missouri								
0	If manufactured on	site at OSU	, provide deta	ails of facilitie	es and restricted acc	ess.			
14	Name of supplier:								
	Same as Manufactu	urer (custom	n synthesis)						
15	Summarize preclini new drug (IND) nur	cal and early nber):	y human stud	lies (for studi	es that are required	to have an investigat	ional		
BaP is one of the most extensively studied PAH environmental contaminants. BaP is a skin carcinogen in the rodent 2-stage model involving dermal application and promotion by TPA ^{1,2} . In addition to dermal exposures, BaP has been documented as an animal carcinogen following oral or inhalation exposures. Target tissues include liver, forestomach, esophagus, auditory canal and oral cavity. Occupational exposures in humans are associated with increased incidences of cancers of the lung, skin and bladder ² . Animal studies in mouse and rat confirm the carcinogenic potential of BaP when administered by the oral route, a mimic of human exposure ² . Dose-dependent appearance of tumors can be observed in the forestomach, esophagus, tongue and larynx in a somewhat reliable manner. A summary of animal studies in which BaP was administered by the oral route is provided in the table below, the dose information was converted to mg/kg for ease of comparison. The summary only includes studies which evaluated untreated control animals as a negative control. Animal Studies with Orally Administered Benzo[a]pyrene									
	Species	Dose	Route;	Duration	Tumor	Reference			
		(mg/kg)	Regimen		Observations	(all in Ref 2)			
	Mouse,A/J				Forestomach	Weyand et al.,			
		0	Oral,	260 days	tumors	1995			
		550	Diet		0/21 (0%)	Chem Res Toxicol			
		3,350			5/25 (20%) 27/27 (100%)	8(7): 949-954			
	Mouse, B6C3F1				Forestomach	Culp et al., 1998			
		0	Oral,	2 years	tumors	Carcinogenesis			

1/48 (2%)

19(1): 117-124

		25 100			3/47 (6%) 36/46 (78%) 46/47 (98%)			
	Mouse,Swiss	0 50	Oral 2X/week, 4 weeks	27 weeks	Forestomach tumors 0/10 (0%) 10/10 (100%)	Badary et al., 1999 Eur J Canc Prev. 85 435-440		
	Mouse, Muta	0 75 125	Oral, 5 consec. days	41 weeks	Forestomach tumors 0/8 (0%) 10/10 (100%) 10/10 (100%)	Hakura et al., 1998 Regul Toxicol Pharmacol 27(3): 273-279		
	Rat, Sprague Dawley	0 6 39	Oral, 1x/9 days 5X/week	Lifespan	Combined tumors 3/64 (4.7%) 3/64 (4.7%) 10/64 (15.6%)	Brune et al., 1981 J Canc Res Clin Oncol 102(2): 153-157		
	Rat Crl:CD	0 63	Oral, 1x/week 8 weeks	49 weeks	Mammary Tumors 1/30 (3%) 11/30 (37%)	El-Bayoumy et al.,1995 Carcinogenesis 16(2):431-434		
	The mouse study of 100,000 times grea in tumor incidence. 6 mg/kg did not res	f Culp et al., ter than the . This is simil sult in an inc	1998 (see ab dose in our r ar to the rat s rease in tumo	ove Table) ut nicrodose stu study of Brun ors when anin	tilized the lowest ex udies) which did not le et al., 1981 (see a mals were monitore	posure with 5 mg/kg (produce a significant bove Table) in which d for their lifetime.	a dose increase a dose of	
16	Will an FDA-approv population that is d provide justification	red drug be a lifferent fror n and safety	administered n what has be information:	for an indica een approved	tion, dose, route of d for the marketed p	administration, or sul product? If "yes", exp	oject lain and	
17	Provide the plan for FDA-approved drug	r the storage s, and/or bi	e, dispensing, ologics:	handling, inv	ventory control, and	disposal of investigation	ional,	

Preparation Location: The lab where the capsules are prepared (LPSC 383) is not a radiopharmacy. Because these capsules are created solely for the purposes of this study and are not to be considered a therapeutic drug, they are not made to GMP standards but will be prepared with the highest quality, consistency and precision possible. Room 383 is a locked, secure laboratory, and no other activities occur in this space besides those related to BaP handling and capsule preparation. [name] and [name] are the only persons with keys to access this space.

Capsules intended for human use will be prepared in a clean hood dedicated solely to capsule preparation. Concentrated ¹⁴C-BaP stock solution is not diluted in the same area as capsule preparation. The hood where capsule preparation is performed will be surveyed for radioactivity by taking swipes and evaluating with liquid scintillation counting. The capsule preparation hood will be sterilized with bleach and alcohol, and all work surfaces will be covered with fresh, plastic backed laboratory bench paper. All pipettes are calibrated, dedicated to this procedure, and only used with sterile, filter pipette tips. All Hamilton syringes were purchased new, checked for accuracy, and dedicated to this project.

Material storage & preparation: Prior to use, empty Solaray[®] capsules and pharmaceutical grade lactose monohydrate NF (Spectrum Chemical Mfg. #61-1730890) are stored in an airtight bag in a gasket sealed plastic box, in a cabinet in a lab that does not utilize scintillation-detectable radioactivity or human tissues. This box contains all microdosing supplies in an area separated from traditional laboratory supplies.

The [¹⁴C]-BaP is shipped as a concentrated solution (0.10 mCi/ml; specific activity = 26 nCi ¹⁴C/nmol BaP = 0.103 nCi/ng) in toluene. This concentrated solution is stored in sealed containers as received from the supplier at -80°C in a secure carcinogen laboratory in LPSC 383. In order to ensure radiochemical purity (greater than or equal to 98% for the purified concentrated stock) and to prepare a diluted sample suitable for human consumption, the compound is collected as a single peak from an HPLC run. The identity of the compound is confirmed by co-elution with a non-radioactive standard.

Phenanthrene is obtained from the Oregon State University Superfund Core D Chemical Repository and is >99.5% pure as documented by GC-MS/MS.

Two different working stock solutions will be prepared by diluting the 0.10 mCi/mL [¹⁴C]-BaP concentrated solution:

• Stock solution #1 will contain 50 ng [¹⁴C]-BaP /25 μ L = 2 ng/ μ L (5.4 nCi ¹⁴C/25 μ L = 0.2 nCi/ μ L). For example, to make 4 mL of stock solution #1, 8 μ L of the 0.10 mCi/mL solution will be aliquoted into a clean vessel. Toluene is carefully evaporated off, and the [¹⁴C]-BaP aliquot resolubilized into 4 mL 95% food grade ethanol. The radioactivity will be checked with a liquid scintillation counter and

adjusted to the target concentration if needed.

• Stock solution #2 will be prepared in the same manner as stock solution #1 with the addition of 50 ng/ μ L non-radioisotope labeled phenanthrene solubilized in the 95% food grade ethanol for a final concentration of 50 ng [¹⁴C]-BaP + 1250 ng phenanthrene/25 μ L = 5.4 nCi ¹⁴C/25 μ L.

Stock solutions will be aliquoted into clean 2 mL amber glass vials and stored under argon at -80°C. Each stock solution is checked for \ge 95% [¹⁴C]-BaP radioisotope purity on a quarterly schedule throughout the study. Stock solutions will be checked for both purity and concentration on UPLC using UV detection for phenanthrene and BaP and radioisotope detection for [¹⁴C].

Capsule preparation, verification and storage: [name] will prepare the capsules. As an added safety measure, [name] or [name] will accompany [name] during capsule preparation for quality control and to ensure that a second trained individual is always present to assist, confirm and verify capsules are produced per specified SOPs.

Each capsule will contain only the [¹⁴C]-BaP or [¹⁴C]-BaP plus phenanthrene and lactose as an excipient. Empty vegetarian capsules, size 0, composed of vegetable cellulose, will be opened and held in a microtube rack. The empty capsules will be filled with lactose. The 25 μ L aliquot of either stock solution #1 or #2 will be applied to the lactose with a calibrated pipet fitted with a sterile filter tip. The ethanol is allowed to evaporate, and then the capsules are sealed with their caps.

Five (5) capsules will be prepared in each batch: Up to two (2) subjects may participate in a study cycle per week and three (3) capsules will be used for quality control verification.

Capsules for quality control: Immediately after preparation, 3 of the 5 capsules will each be dissolved in 5 ml ultrapure water and 15 ml scintillation cocktail and counted on a liquid scintillation counter. Results will be emailed directly to the director of OSU Radiation Safety (RSO). Once the RSO has determined that the three evaluated capsules are within 10% variance and 10% error, the results are emailed to [name]. [name] will then contact [name] and [name] that the cycle(s) may proceed. If the capsules are not given RSO approval, a new set of capsules will be prepared and the subject(s) will be rescheduled if needed.

Capsules for subjects: Two capsules will be stored in sealed vials in the dark in a zipper-lock plastic bag with silica desiccant at -20°C until subject consumption. The bag will be labeled appropriately (see sample label). Any capsules not used within 1 week will be discarded.

	Dispensing: Capsules will be transported to the Clinical Research Center (407 LPSC) in sealed vials within the labeled zipper-lock plastic bag. The bag will be stored within a plastic box for transportation to the clinic.		
	One (1) capsule containing 50 ng [¹⁴ C]-BaP or 50 ng [¹⁴ C]-BaP plus 1250 ng phenanthrene will be administered to the subject with 100 mL of water by the nurse coordinator at the start of the study cycle.		
	Inventory control: Information including number of capsules, date of preparation, and operator are recorded immediately after capsules are prepared. Date of consumption and disposal of test capsules are recorded on day 1 of the cycle. If test capsules do not pass approval by the OSU radiation safety officer, the information is still recorded and a new set of capsules will be prepared.		
	Disposal: Capsules that are not needed, expired or rejected for human use will be disposed of in the radiochemical dry waste at Oregon State University.		
	Please see IRB Protocol 8233 for lactose, capsule, and [¹⁴ C]-BaP quality assurance documents.		
	Does the use of the test article involve a route of administration or dosage level, use in a subject		
18	population, or other factor that significantly increases the risks (or decreases the acceptability of the risks) associated with its use? If "yes", explain:		
	As noted above, the use of [¹⁴ C]-BaP and phenanthrene is not intended to be therapeutic. The great majority of exposure (>95%) of the larger molecular weight PAHs, such as BaP, is through the diet in a variety of foods including breads and cereals, grains, vegetables and smoke-cured or barbequed meats ² . Dietary intakes of total PAHs in the U.S./North America have been estimated at 160-3,000 ng/day with BaP alone at 270-700 ng/day. In Asia, dietary levels of total PAHs are estimated at 55,00 ng/day ²⁴ . A 2005 report from the FAO/WHO Joint Expert Committee on Food Additives and Contaminants listed a mean BaP daily dietary intake of 270 ng (70 Kg individual) with 700 ng as a high-level intake ¹ . The European Union maximum limit for BaP in smoked meats is 5,000 ng/Kg fresh weight. The dose of 50 ng would be the equivalent of approximately 10 g of smoked meat at the EU allowable limit. Compiling all of the animal data, a Virtually Safe (Lifetime) Dose (VSD) of 42-350 ng/person/day has been established as the best estimate for a lifetime exposure to BaP producing no more than 1 cancer per million people ²⁻⁴ . Therefore, based on the chemical mass involved in microdosing (significantly lower than background exposure and levels determined to be VSD), this study poses de minimus risk to subjects. As noted above, the single dose of phenanthrene (1250 ng), a non-carcinogenic PAH, in the binary mixture is <15% the average daily dietary exposure (9350 ng) ²⁴ .		

Ø	 Potential attachments triggered by this section: Investigator brochure Approved labeling Package insert Documentation of quality or purity or Certificate of Analysis "Safe to Proceed" from the FDA Correspondence from the FDA Letter from the FDA or industry sponsor setting forth the IND number 			
SECTION	1 25 - Dietary Supplements	Yes	No	N/A
1	 A dietary supplement is a product taken by mouth that is intended to supplement the diet and that contains one or more "dietary ingredients". The "dietary ingredients" in these products may include: Vitamins Minerals Herbs or other botanicals Amino acids Other substances found in human diet, such as enzymes In some cases, dietary supplements or substances generally recognized as safe (GRAS) are considered to be drugs when they are used to diagnose, cure, mitigate, treat, or prevent disease. Under FDA regulations, research that involves use of a drug other than the use of a marketed drug in the course of medical practice must have an Investigational New Drug (IND) Application, unless the study meets one of the exemptions from the IND requirement.			
Q	Guidance and decision trees on Drugs, Biologics, and Dietary Supplements			
1	Are one or more dietary supplements being studied as part of this project?		⊠ Skip to section 26	
2	Name of dietary supplement (include generic and trade name, if applicable):			
3	Approval Status (e.g., FDA Approved, FDA Approved/Unapproved Use, not FDA approved):			

0	If a dietary supplement is being used in the study as a drug, the study is regulated by the FDA. Please see the Guidance on Drugs , Biologics , and Dietary Supplements for additional information.		
4	Has an IND application been submitted to the FDA?		
5	If no, provide justification:		
6	Chemical formula:		
7	Dosage strength(s):		
8	Rationale for choosing the drug or substance dose:		
9	Method/route of administration:		
10	Mechanism of action:		
11	Known drug interactions:		
12	Manufacturer/Sponsor:		
13	Manufacturer/Sponsor Location:		

14	Name of supplier:			
15	Summarize preclinical and early human studies (for studies with an IND):			
16	Will an FDA-approved drug be administered for an indication, dose, route of administration, or subject population that is different from what has been approved for the marketed product? If "yes", explain and provide justification and safety information:			
17	Provide the plan for the storage, dispensing, handling, inventory control, and disposal of the dietary supplement:			
18	Does the use of the test article involve a route of administration or dosage level, use in a subject population, or other factor that significantly increases the risks (or decreases the acceptability of the risks) associated with its use? If "yes", explain:			
Ø	 Potential attachments triggered by this section: Investigator brochure Approved labeling Package insert Certificate of Analysis or other documentation of quality/purity "Safe to Proceed" from the FDA Correspondence from the FDA Letter from the FDA or industry sponsor setting forth the IND number 			
SECTION	N 26 - Medical Devices	Yes	No	N/A
•	 A medical device is an instrument, apparatus, implement, machine, contrivance, implant, in vitro reagent, or other similar or related article, including a component part, or accessory which is: recognized in the official National Formulary, or the United States Pharmacopoeia, or any supplement to them, 			

	• intended for use in the diagnosis of disease or other conditions, or in the cure, mitigation, treatment,		
	or prevention of disease, in man or other animals, or		
	 Intended to affect the structure or any function of the body of man or other animals, and which does not achieve any of its primary intended purposes through chemical action within or on the body of 		
	man or other animals and which is not dependent upon being metabolized for the achievement of any		
	of its primary intended purposes.		
Q	Guidance and decision trees on medical devices		
1	Are one or more medical devices being studied as part of this project?	SKIP to section	
		27	
2	Indication if data related to the safety or efficacy of the device will be collected:		
3	Rationale for choosing the device to be used:		
4	Device description:		
	The device description can include:		
	 pictures of the device (where applicable); 		
	 physical, chemical and/or biological processes/principles used by the device to generate device output, 		
	IT applicable;		
	 physical and biological characteristics of the device output, if applicable, evolution of the user interface and/or how the device interacts with other devices or with the user 		
A	(medical professional and/or patient);		
	• explanation of the materials used in the device;		
	• a brief explanation of how the device is manufactured (where necessary);		
	• discussion of the mechanism of action and how the device and/or, if applicable, device output is used;		
	• for an IVD, detailed technical description of your device including instruments, reagents, components,		
	software, principles of operation, and accessories (if there are changes to a previously cleared or		
	approved device, then you should describe these changes);		

	 discussion of the scientific basis for development of the device or an explanation of expected clinical utility; In addition to pictures and a written description, other information about the clinical use of the device, such as a surgical technique guide or video of how the device is used in the clinical setting, may be helpful. 		
5	Proposed Intended Use/Indications for Use:		
•	 Use description can include: identification of the disease or condition the device is indicated to prevent, mitigate, screen, monitor, treat, or diagnose; identification of the target population; part of the body or type of tissue to which applied or with which the device is interacting; frequency of use; physiological use; Statement of whether investigators intend to commercialize or market the device; statement of whether the device is intended for prescription and/or over-the-counter use; For an IVD device, this information should include a detailed draft of the intended use of the device including the intended use population, the analyte/condition to detect, and the assay methodology. 		
6	Is there an intent to commercialize or patent the device?		
0	If there is commercialization intent or if investigators hold IP rights or interests in this device, it is considered a financial interest that should be disclosed in the conflict of interest section of the protocol. Additional disclosures may be required in the consent form.		
7	Will the device(s) be stored in a locked environment under secure control with limited access and in an area of the PI's control?		
8	Will proper instructions on the use of the device will be provided to the subjects?		
9	Will a log be kept regarding the receipt, use, and/or dispensing of the device and the disposition of remaining devices at the conclusion of the investigation?		
10	Will the device be labeled in accordance with the FDA's requirements?		
Ø	Label that will be placed on the device; including an indication of single-use or directions for sterilization between uses.		

SECTIO	N 27 - Food or Beverages	Yes	No	N/A
0	If food or food extract will be used as a drug, complete the drug section above instead.			
0	 21CFR172: Food Additives Permitted For Direct Addition To Food For Human Consumption (FDA approved) 21CFR182: Substances Generally Recognized As Safe (FDA affirmed) 21CFR184: Direct Food Substances Affirmed As Generally Recognized As Safe (FDA affirmed) 21CFR186: Indirect Food Substances Affirmed As Generally Recognized As Safe (FDA affirmed) FEMA GRAS LIST: Flavor & Extract Manufacturers Association, Flavor Ingredient Library (FDA consulted and had no questions) EAFUS: Everything Added to Food in the United States. Inclusion on this list does not indicate approval or affirmation – it simply provides the references and regulations pertaining to a food ingredient 			
SECTIO	N 27.1 - Food as Courtesy or Compensation	Yes	No	N/A
1	Does the study involve providing participants with commercially purchased food intended as a courtesy or compensation?	\boxtimes	Skip to section 27.2	
2	If the study involves providing participants with commercially purchased food intended as a courtesy or compensation, will allergen information (clear labeling or menu with ingredients listed) be provided to the participants? If no, explain why:			
SECTIO	N 27.2 - Food as Intervention	Yes	No	N/A
1	Does the study involve participants ingesting, tasting, or smelling a food or beverage, or a component thereof for the purpose of research?		⊠ Skip to section 28	
2	Name of food, beverage, or component thereof:			
3	Supplier (e.g., manufacturer name, grocery store, restaurant):			
4	Is this study a taste and food quality evaluation or consumer acceptance study?			

5	Will participants consume wholesome foods without additives?		
0	21CFR172: Food Additives Permitted For Direct Addition To Food For Human Consumption (FDA approved)		
6	Will the food or beverage consumed contain only ingredients that are at or below the level and for a use found to be safe by the Food and Drug Administration?		
7	Will the food or beverage consumed contain only agricultural chemicals or environmental contaminants at or below the level found to be safe (or approved) by the Environmental Protection Agency or the Food Safety and Inspection Service of the U.S. Department of Agriculture?		
8	Has there been a determination by the FDA that the product is Generally Recognized as Safe (GRAS)?		
9	If yes, provide GRAS number:		
10	Has the determination of GRAS been self-affirmed as a result of published safety data?		
11	Is the food, beverage, or component food-grade and intended for use in humans? If yes, provide documentation. If no, explain and indicate how safety for use in humans is known and attach documentation that demonstrates substantial equivalence to ingredients found in the food supply:		
Ø	Certificate of Analysis from the manufacturer; package insert		
0	All GRAS substances are food-grade. The same substance at another grade is not GRAS.		
12	Risks to subjects are minimized by ensuring that the proposed products are food-grade. If product is not food-grade, compare the analysis to the same product in the USP Food Chemicals Codex and provide an assessment of whether the proposed product is substantially equivalent:		
13	Provide the plan for the storage and handling of the food:		
Ø	GMP certificate or food-grade certificate that indicates that the product can be lawfully used in the US food supply Documentation that the product is an approved food additive (21 CFR 172) Safety data if GRAS status is self-affirmed		

SECTIO	N 28 - Radiation	Yes	No	N/A
0	The Radiation Safety Officer will review this submission.			
1	Does the study involve exposing participants to radiation?		□ Skip to section 29	
2	Will any participant be asked to undergo an x-ray procedure (including radiographic and DEXA) while in this study?		\boxtimes	
2a	All x-ray procedures are for research use only, and will not be used for medical screening or diagnosis.			
2b	If diagnostic x-ray scans are performed for medical screening, and all procedures are routine, standard, clinical procedures.			
2c	All participants receiving a diagnostic radiation procedure would have the same procedure for clinical reasons even if they were not in this study.			
3	Will radioactive materials (including nuclear medicine, metabolic, nutrition, toxicity, or drug studies) be administered to any participants as part of this study?	\boxtimes		
3a	All procedures involving administration of radioactive materials are routine standard, clinical procedures prescribed by a physician.		\boxtimes	
3b	All participants receiving a radioactive material would have the same procedure for clinical reasons even if they were not in this study.		\boxtimes	
4	Summarize the "authorized users" training and experience in the use of (ionizing) radiation-emitting devices and/or radioactive materials with human participants:			

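### The 14C activity figures disagree across sections and the SAP states no mixture-versus-alone comparison; a possible difference between the two stocks merits one sensitivity analysis, no more

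*Combined protocol and SAP*

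**What the plan says.** **Stocks and capsules (Section 24 item 17).** "Two different working stock solutions will be prepared by diluting" the concentrated labelled solution. Stock #1 holds BaP alone, and stock #2 is made the same way with phenanthrene added. Each capsule receives a 25 µL "aliquot of either stock solution #1 or #2 will be applied to the lactose with a calibrated pipet".

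**Safeguards.** Stock radioactivity is counted by liquid scintillation and "adjusted to the target concentration if needed". In addition, "Stock solutions will be checked for both purity and concentration on UPLC using UV detection for phenanthrene and BaP and radioisotope detection for" 14C. Capsules are made five to a batch: "Up to two (2) subjects may participate in a study cycle per week and three (3) capsules will be used for quality control verification". A study cycle proceeds "Once the RSO has determined that the three evaluated capsules are within 10% variance and 10% error". The target for that check is not restated there. The inventory paragraph says "Information including number of capsules, date of preparation, and operator are recorded"; it does not name the counts.

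**Activity figures.** Specific activity is 27 µCi/µmol in Section 24 item 2 and Section 28 item 7a. In Section 24 item 17 it is 26 nCi/nmol, which is the same unit, with the per-mass value given as "0.103 nCi/ng) in toluene". Item 17 states 5.4 nCi per 50 ng in 25 µL and, on the same line, 0.2 nCi/µL. Section 28 item 7b gives 0.0000054 mCi (5.4 nCi). Section 37 item 3 gives 10.4 nCi for two cycles.

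**Hypothesis and analysis.** Section 13 predicts that phenanthrene will not change BaP metabolites, Cmax or elimination rate. The SAP regresses pharmacokinetic parameters on dose, then compares a line through the origin with a Michaelis-Menten curve by BIC. It mentions neither the mixture condition nor measured dose.

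**Carried-over controls (Section 20).** A subject who completed the 50 ng cycle of protocol 8233 within the prior 12 months takes only the mixture cycle here.

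**The concern.** There are three linked issues.

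1. The activity figures are used to describe the dose, to set the implied QC target and to convert 14C to BaP mass. They do not agree with each other, so two analysts following different sections would report different mass concentrations.
2. The analysis that would answer the study question is not written down.
3. The AMS signal scales with the 14C administered, and stock is completely aliased with condition. Any residual activity difference between the stocks therefore enters the mixture/alone ratio of Cmax and of metabolite amounts as if phenanthrene had caused it. If one preparation serves a condition throughout, the difference does not average out over subjects; with several preparations, part of it does. Under linear kinetics, elimination rate and metabolite fractions are unaffected.

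**Working it through.** **A. Activity per capsule.** The molecular weight of C20H12 is 252.32; 26/0.103 = 252.4 confirms that this is the conversion used.

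| Source | Calculation | nCi per capsule |
|---|---|---|
| Stated, Section 24 item 17 and Section 28 | – | 5.4 |
| From 27 nCi/nmol | 50 × 27/252.32 | 5.35 |
| From 26 nCi/nmol | 50 × 26/252.32 | 5.15 |
| From 0.2 nCi/µL | 25 × 0.2 | 5.0 |
| Example recipe, before adjustment | 8 µL × 100 nCi/µL ÷ 4000 µL × 25 µL | 5.0 |
| Section 37 total, halved | 10.4/2 | 5.2 |

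The stated 5.4 is reproduced, after rounding, from 27 but not from 26. Conversely, 5.4 nCi at 0.103 nCi/ng is 52.4 ng. Two cycles give 10.70 nCi at 27, 10.30 at 26 and 10.8 at 5.4 each; Section 37 has 10.4. The conversion difference is 27/26 = 1.038, or 3.8%.

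**B. SAP against hypothesis.** The only BaP dose in this protocol is 50 ng (Section 24 item 7). With one dose level the regressor does not vary, so a slope on dose cannot be estimated. Even with doses from elsewhere, the slope would describe linearity in BaP dose, not the effect of phenanthrene.

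**C. Effect of a stock gap.** The documents give no gap, no within-subject CV and no test for this comparison. The following are assumptions: a paired t-test on log values, n = 7 (the completion goal in Section 14), two-sided alpha 0.05, the same gap for every subject, and gaps of 3% and 5%.

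σw = √ln(1 + CV²); SE = σw × √(2/7); critical t (6 df) = 2.447. The rejection rate comes from the noncentral t with noncentrality ln(gap ratio)/SE.

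| Within-subject CV | SE | 3% gap | 5% gap |
|---|---|---|---|
| 10% | 0.0533 | 7.6% | 12.1% |
| 20% | 0.1059 | 5.6% | 6.8% |
| 30% | 0.1569 | 5.3% | 5.8% |
| 40% | 0.2059 | 5.2% | 5.5% |

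For a true 20% increase at CV 10%, power is 81%. It falls to 67% (3% gap) or 56% (5% gap) if the gap opposes the effect, and rises to 91% or 95% if the gap aligns with it.

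The example stock volume would fill 4000/25 = 160 capsules, so one preparation per condition is feasible. The documents do not say that this is what happens.

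**D. Price of normalising.** Dividing by a three-capsule mean multiplies the SE by √(1 + (c²/3)/σw²), where c is the capsule CV, assumed to be 2–5%. If subjects share batches in pairs (three pairs and one single), c²/3 is multiplied by 13/7. The SE rises as follows:
- CV 10%: 0.7–4.1%, or 1.2–7.5% if shared.
- CV 20%: 0.2–1.1%, or 0.3–2.0% if shared.

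If only n pairs have counts, the 95% CI width is multiplied by √(7/n) × t(n−1)/2.447. This gives 1.13, 1.34, 1.72 and 2.69 for n = 6, 5, 4 and 3.

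**The case against.** Much of the case against stands.

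- Separate stocks are an ordinary way to make a mixture condition. The plan counts and adjusts the stock, checks concentration by UPLC, uses a calibrated pipet and counts three of every five capsules. No gap has been shown.
- The size of the effect rests on assumed values. Section 20 reports little within-person variation, which points to the more sensitive rows of the table, but it gives no number. At CV 30–40% the effect nearly vanishes.
- The inventory list opens with the word *including*, and the section refers to SOPs and to quality documents held under protocol 8233, none of which is in this file. A reader might infer that the QC counts are discarded; the documents do not show that.
- The recipe is labelled an example and is adjusted afterwards. Its 5.0 nCi is in line with the rounding of 5.4/25 = 0.216 to 0.2, so it is weak evidence of a separate error.

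What survives is narrower. The safeguards limit a gap without removing it, and gaps of 3–5% sit inside a 10% limit. Rounding does not reconcile 26 with 27, 5.15 with 5.4, or 10.4 with 10.8. The missing comparison is untouched by any of these arguments.

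**Conclusion.** Two things are wrong as written: the activity figures contradict one another, and the SAP has no analysis that tests the mixture hypothesis. The 26/27 conflict is worth 3.8% on absolute levels. It cancels in the within-subject ratio when both cycles use the same value; nothing in this file fixes that value for control cycles carried over from protocol 8233.

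The stock aliasing is a real but modest weakness. A reader might infer that the study comparison is biased, or that dose ratios between 0.9/1.1 = 0.82 and 1.1/0.9 = 1.22 are to be expected. The documents do not support either: that range is only the extreme if the 10% error limit is read as each batch mean lying within 10% of target, and the upstream checks make a large gap unlikely. On the assumptions above, a 3–5% gap is noticeable at CV 10% (7.6–12.1% false change) and close to negligible at CV 30–40% (5.2–5.8%). That justifies a sensitivity analysis, not a change to the primary one.

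Overall severity is minor to moderate, with medium confidence.

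**What to change.** 1. **Reconcile the figures.** Bring the specific activity, per-capsule activity, concentration per µL, example recipe and two-cycle total into agreement across Section 24 items 2 and 17, Section 28 item 7 and Section 37 item 3. No value is chosen here. Use one documented specific activity per labelled lot for every 14C-to-mass conversion, including 8233 control cycles, and state in the capsule QC paragraph the reconciled target for the 10% check.
2. **State the comparison.** Add to the SAP, as the primary analysis, the within-subject mixture-versus-alone comparison of log Cmax, metabolite amounts and elimination rate, un-normalised and in all subjects.
3. **Add one sensitivity analysis.** Keep the batch QC counts with the study data. Divide Cmax, AUC (if reported) and metabolite amounts by that batch's mean QC activity, only in subjects with counts for both cycles, so that no pair is half-corrected. Leave elimination rate and metabolite fractions un-normalised.

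The cost is wording plus arithmetic on counts already made. The downside of item 3 is slight added noise (SE up 0.2–7.5% over within-subject CVs of 10–20%) and a CI wider by 13%, 34%, 72% or 169% if only 6, 5, 4 or 3 pairs have counts. Section 20 sets no cap on carried-over subjects, so those smaller numbers are possible. This is why the normalised analysis should stay secondary.
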